8.4.6 Compliance

Subject compliance with study drug will be assessed by counting capsules that are returned at each study visit. Subjects whose actual capsule consumption differs from their expected capsule consumption by more than 20% should be queried by site personnel about reasons for not using study drug as directed, and site personnel should plan any corrective action as necessary. Subjects who remain noncompliant with study drug dosing despite corrective action by site personnel may be withdrawn from the study.

8.4.7 Drug Storage and Drug Accountability

All unused study drug must be stored in its packaging at controlled room temperature, 15 to 25°C (59 to 77°F) with excursion to 30°C (86°F), in a dry, secure area. Access to drug storage areas should be limited to the investigator and designated staff involved with the study. All used and unused drug must be maintained at the study site and made available for audits by VIVUS personnel or their designee.

It should be noted that phentermine, one component of the VI-0521 combination is a Schedule IV controlled substance. The investigator should take all appropriate measures to control access to and dispensing of study drug.

The investigator must maintain records documenting the amount, condition, and date of delivery

of all study drug received from the sponsor. In addition, all drug dispensed to study subjects during the course of the study must be recorded on the appropriate accountability forms. Subjects must be instructed to return all empty containers and all unused medication in its original packaging, and sites must make an accounting of drug use by each subject. No study drug, used or unused, may be discarded. All used and unused drug must be returned to the sponsor or designated representative upon completion of the study.

8.5 Concomitant Medications

8.5.1 Excluded Medications

Subjects may not use any of the following medications during participation in this study. Subjects who develop a need for any of these medications must be discontinued from the study:

- Anticonvulsants used for treatment of seizure disorder, including barbiturates, benzodiazepines, GABA analogues, hydantoins, phenyltriazines, succinimides, and other agents (valproic acid and its derivatives, carbamazepine and its derivatives, zonisamide, and felbamate);
- Tricyclic antidepressants, MAOIs, lithium, levodopa, and dopamine receptor agonists;
- Carbonic anhydrase inhibitors;
- Insulin, sulfonylureas (SFUs), GLP-1 agonists, SGLT-1 inhibitors, and SGLT-2 inhibitors;
- Chronic systemic steroids (i.e. glucocorticoids, anabolic steroids) other than oral contraceptives;
- Treatment for hyperactivity disorder; or
- OTC, prescription medications, herbal agents and dietary supplements used with the intention to lose body weight.

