6.0 STUDY DESIGN

In this multicenter, randomized, double-blind, placebo-controlled, parallel-design study, approximately 200 subjects will be enrolled at approximately 20 sites in the United States. Subjects will be randomly assigned in a 1:1:2 ratio to placebo, $N= 50$; mid-dose (PHEN/TPM 7.5 mg/46 mg), $N= 50$; or top-dose (PHEN/TPM 15 mg/92 mg), $N=100$, of VI-0521, to be taken orally once daily in the morning. Randomization will be stratified by age (12-14 vs 15-16 years old) and gender. The study will consist of a screening period of up to 28 days, followed by a 56-week treatment period.

[figure not shown]
Subjects will be instructed to follow a mild hypocaloric diet modification program representing a 500-calorie/day deficit and to implement a family-based lifestyle modification program for adolescents, as tolerated, throughout the study period. The lifestyle program will include physical activity, behavior change, and family support. The same lifestyle modification program, specific to this population, will be implemented across all sites. Study drug will be titrated as described in Section 8.4.1.

Subjects who are unable to tolerate the assigned dose may be treated at a reduced dose level or may take a drug holiday as defined in Section 8.4.4. In addition, for growth monitoring, investigators will monitor rates of weight loss in treated subjects. For subjects with baseline BMI 95-98th percentile, reduce study drug dosage when BMI is < 85th percentile or when weight loss exceeds an average of 2 lbs (0.9 kg) per week. For subjects with baseline BMI $\geq 99^{th}$ percentile, reduce study drug when weight loss exceeds an average of 2 lbs (0.9 kg)/week.

All subjects will return at approximately 4-week intervals for study assessments. All female

subjects will undergo a pregnancy test at each visit. Subjects who discontinue study drug during the study will be encouraged to remain on study (off study drug) for continued follow-up by attending all remaining visits and have all study-related procedures performed, and to return at the 56-week time point for measurements and evaluations. For those who choose to completely withdraw from the study at any point, the end of study (Week 56) procedures should be completed.

Figure 1. Schematic Diagram of Study Design

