8.3 Breaking the Blind

Study drug must not be unblinded during the study unless it is considered absolutely necessary

by the investigator for the management of an adverse event or other medical emergency. Under such conditions, investigators will first contact the medical monitor when deciding to unblind a subject and if unblinding is deemed medically necessary the identity of the study treatment may be obtained via the IWRS. Any subject whose treatment assignment has been unblinded must be withdrawn from the study.

Investigators are also required to ensure that any potential SAEs are reported according to the requirements outlined in Section 11.1.5 and provide a written report to VIVUS or designee within 7 days to document the reason for unblinding.

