8.6 Treatment of Diabetes

Subjects who develop type 2 diabetes during the course of the study will be provided with blood glucose meters and supplies and will be provided appropriate usage instructions. They will be instructed to measure a fasting morning glucose daily and to record the results in the blood glucose and hypoglycemic event log. Diabetic subjects will bring their meters and logs to each visit.

If concomitant antidiabetic therapy is determined necessary, metformin is suggested as the initial therapy for newly-emergent type 2 diabetes unless contraindicated in a specific subject. Insulin secretagogues, including SFUs and meglitinides, either alone or in combination with other medications, should be reserved for subjects who cannot achieve adequate control with other modes of treatment. Insulins and incretins are prohibited, and subjects requiring treatment with these medications must be discontinued from the trial. Subjects whose blood glucose cannot be adequately controlled with the concomitant treatments allowed in this trial should be maintained in the study but discontinued from treatment, and referred back to their primary healthcare provider for more intensive treatment (see Section 7.3).

During treatment, subjects whose fasting blood glucose is less than 72 mg/dL on 2 or more occasions, or who experience any signs or symptoms associated with hypoglycemia, should have their antidiabetic therapy reevaluated.

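### Protocol 8.3, 8.5.1 and 8.6 order exit from the study where the rest of the plan stops drug and keeps follow-up; 8.5.1 and 8.6 also contradict each other on sulfonylureas

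*Protocol*

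**What the plan says.** Three sections make exit from the study compulsory:

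- 8.5.1, excluded medication: "Subjects who develop a need for any of these medications must be discontinued from the study".
- 8.3, unblinding: "Any subject whose treatment assignment has been unblinded must be withdrawn from the study".
- 8.6, insulins and incretins: "subjects requiring treatment with these medications must be discontinued from the trial".

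A fourth, 8.4.6 on noncompliance, only permits it: "Subjects who remain noncompliant with study drug dosing despite corrective action by site personnel may be withdrawn from the study".

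Elsewhere the protocol separates stopping drug from leaving the study. Section 6.0 states: "Subjects who discontinue study drug during the study will be encouraged to remain on study (off study drug) for continued follow-up". Sections 7.3 and 8.4.4 repeat this, and 8.7 lets subjects with uncontrolled blood pressure keep attending off drug. Section 8.6 itself says that subjects not controlled on the permitted antidiabetic drugs "should be maintained in the study but discontinued from treatment".

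On sulfonylureas, the 8.5.1 list includes "Insulin, sulfonylureas (SFUs), GLP-1 agonists, SGLT-1 inhibitors, and SGLT-2 inhibitors". Section 8.6 says: "Insulin secretagogues, including SFUs and meglitinides, either alone or in combination with other medications, should be reserved for subjects" whom other treatment does not control.

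**The concern.** Protocol 12.5.2 and SAP 5.2 commit the trial to following subjects who stop treatment, with emphasis on weight and height at Week 56. SAP 6.6.1 depends on that follow-up: subjects who stop drug but are still measured supply the imputation for those who are not. If there are too few of them (no threshold is given), the primary analysis moves to a washout imputation. A rule that removes subjects from the study works against that aim.

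Three things are at stake:

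- A subject whose visits have ended may be less likely to come back at Week 56. That would be one fewer donor and one more value to impute.
- Off-drug measurements between exit and Week 56 are lost. So are the vital signs, PHQ-9 and C-SSRS scheduled at each visit in Appendix 1. Safety is a primary objective, and under 11.3 adverse event reporting closes 28 days after the last day of study participation.
- A site treating a subject who needs a sulfonylurea has two instructions that cannot both be followed.

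**Working it through.** **Step 1. The instructions side by side**

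| Section | Situation | Instruction |
|---|---|---|
| 8.3 | Unblinded | Must leave the study |
| 8.5.1 | Needs an excluded drug | Must leave the study |
| 8.6 | Needs insulin or an incretin | Must leave the trial |
| 7.3 | Needs excluded treatment (citing 8.5) | Participation *may* be discontinued |
| 8.6 | Glucose uncontrolled on permitted drugs | Off drug, stays in study |
| 8.7 | Blood pressure uncontrolled | Off drug, may keep attending |
| 6.0, 7.3, 8.4.4 | Stops drug | Encouraged to keep attending |

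Sections 8.5.1 and 7.3 differ on *must* versus *may* for the same reason. Within 8.6, a subject uncontrolled on permitted drugs stays in the study and is referred for more intensive treatment. That treatment could be insulin or an incretin, which the preceding sentence makes a reason for trial exit.

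**Step 2. What study exit entails**

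Under 7.3 and 9.1.4 the subject completes Visit 16 procedures on leaving, and the last item in 9.1.4 ends participation. Section 9.2 closes the study period once early termination is completed. After that, 7.3 has the site ask the subject back at about Week 56 for at least weight and height, and 9.1.4 has it attempt contact. No single sentence says that the 4-weekly visits stop; this is the natural reading of 9.1.4 with 9.2.

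**Step 3. Visits lost on that reading**

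Visits fall every 4 weeks, so exit at week *w* removes (52 − *w*)/4 visits before Week 56:

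- Week 4: (52 − 4)/4 = 12
- Week 16: (52 − 16)/4 = 9
- Week 48: (52 − 48)/4 = 1

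**Step 4. How the primary analysis treats these subjects**

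Under SAP 6.6.1, a Week 56 value obtained after permanent exit from treatment and study is used, and the gap before it is interpolated. Interpolation is described only for that case. Without a Week 56 value, the subject is imputed from retrieved dropouts, or by washout if those are too few.

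**Step 5. The plan's power figure**

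Inputs from protocol 12.2: difference 2 BMI units, SD 2.9, arms of 50/50/100, 30% dropout, leaving 35/35/70. SAP 6.1 gives a two-sided 5% level. For a two-sample t-test the noncentrality is 2 / (2.9 × √(1/n₁ + 1/n₂)).

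- Mid-dose vs placebo, 35 vs 35: 2/0.693 = 2.88, power 81.2% (stated: approximately 80%).
- Top-dose vs placebo, 70 vs 35: 2/0.600 = 3.33, power 91.0% (stated: at least 90%).

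Both reproduce. The calculation already discards 30% of subjects, so rule-based exits within that 30% do not alter it.

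**Step 6. Scale of donor loss, illustration only**

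The documents give none of the following: SD of percent BMI change 8%; 15 of 50 subjects stopping drug (0.30 × 50); 5 of those measured at Week 56; donors taken from the same arm; recall always failing after a forced exit. The SAP 6.6.1 primary text does not say donors are arm-specific; pooled donors would make one loss matter less. Treating the stoppers' mean as the donor mean,

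SE of arm mean = SD × √(0.7²/35 + 0.3²/d), with expected donors d = 5 × (1 − k/15) after k forced exits.

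- k = 0: 8 × √(0.014 + 0.0180) = 1.43
- k = 1, d = 4.67: 8 × √(0.014 + 0.0193) = 1.46, a rise of 0.03 points
- k = 3, d = 4: 8 × √(0.014 + 0.0225) = 1.53, a rise of 0.10 points

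Over SD 6–10% and 3–7 donors, one exit adds 0.02 to 0.05 points.

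**The case against.** The strongest reply is that the primary endpoint is already protected. Withdrawn subjects are asked back for Week 56 weight and height, the site must attempt contact, and SAP 6.6.1 uses the value if it is recovered. That stands. A reader might infer that these rules rule out a Week 56 value, or that they bias the primary contrast or erode its power. The documents support none of these: they give neither the number of such exits nor the success rate of recall, and the contrast is at Week 56, so lost intermediate visits are not in themselves shown to change it.

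It can also be said that the end of the 4-weekly visits is inferred. That is fair. Section 7.3 speaks of withdrawn subjects who have not continued visits, which leaves room for some who have, and it uses *may* for excluded treatment. This softens the reading but confirms that the sections disagree.

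Third, retaining these subjects brings in BMI values measured on weight-active prohibited drugs or after unblinding. That is a real trade-off, but SAP 6.6.1 would already use such values if recovered.

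Finally, the sulfonylurea conflict is a separate matter and lends no weight to the retention argument. Agreed; it needs correcting on its own account.

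**Conclusion.** The concern holds as a low-priority point to consider on follow-up, and as a plain error on sulfonylureas. Sections 8.3, 8.5.1 and 8.6 compel study exit against the approach taken in the rest of the protocol. The probable consequence is lost off-drug visits, up to 12 for exit at Week 4, together with their safety assessments. This rests on reading 9.1.4 with 9.2.

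The effect on the primary analysis is probably small and cannot be quantified from the documents. The standard-error figures show only that, with arm-specific donors and failed recall both assumed, a single exit would move an arm's standard error by a few hundredths of a percentage point. The stated power is unaffected while total dropout stays within 30%.

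**What to change.** **Protocol 8.3, 8.5.1, 8.6 and the excluded-treatment item of 7.3.** Replace withdrawal from the study or trial with discontinuation of study drug. State that scheduled visits, and at least Week 56 weight and height, continue unless consent is withdrawn. Withdrawal by the subject or parent and termination of the trial would still end participation.

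**Sulfonylureas.** Make 8.5.1 and 8.6 agree: either remove them from the drugs that trigger discontinuation on study, or remove them from the reserve therapy in 8.6.

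**Optional.** Make the same change to the permissive wording in 8.4.6 and the noncompliance item of 7.3. Add one sentence to SAP 6.6.1 confirming that the Week 56 value is used after a prohibited drug or unblinding.

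**Cost.** Wording in three protocol sections and one list item, a few more off-drug visits, and some Week 56 BMI values taken on a prohibited drug or after unblinding. Design, sample size and model do not change.

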8.5.2 Other Restricted Medications

Subjects using hormone replacement therapy (estrogen, thyroid, or other) or allowed antidepressants must be on doses that have been stable for at least 3 months prior to screening. Subjects who develop symptoms indicative of hypothyroidism during the course of the study need not withdraw but should be evaluated and managed as indicated.

Benzodiazepine and non-benzodiazepine sleep medications are permitted, provided that the dosage has been stable for at least 1 month prior to screening, and the frequency of use does not exceed twice a week.

Subjects may not initiate any other organized weight loss program during their participation in this study.

8.5.3 Documentation of Concomitant Medication Use

All concomitant medications, including OTC products and nutritional/herbal supplements, must be listed on the appropriate CRF at study entry. Any changes in concomitant medication use during the course of the study must also be noted on the appropriate CRF.

8.6 Treatment of Diabetes

Subjects who develop type 2 diabetes during the course of the study will be provided with blood glucose meters and supplies and will be provided appropriate usage instructions. They will be instructed to measure a fasting morning glucose daily and to record the results in the blood glucose and hypoglycemic event log. Diabetic subjects will bring their meters and logs to each visit.

If concomitant antidiabetic therapy is determined necessary, metformin is suggested as the initial therapy for newly-emergent type 2 diabetes unless contraindicated in a specific subject. Insulin secretagogues, including SFUs and meglitinides, either alone or in combination with other medications, should be reserved for subjects who cannot achieve adequate control with other modes of treatment. Insulins and incretins are prohibited, and subjects requiring treatment with these medications must be discontinued from the trial. Subjects whose blood glucose cannot be adequately controlled with the concomitant treatments allowed in this trial should be maintained in the study but discontinued from treatment, and referred back to their primary healthcare provider for more intensive treatment (see Section 7.3).

During treatment, subjects whose fasting blood glucose is less than 72 mg/dL on 2 or more occasions, or who experience any signs or symptoms associated with hypoglycemia, should have their antidiabetic therapy reevaluated.

8.7 Treatment of Elevated Blood Pressure

For subjects whose blood pressure requires management, antihypertensive therapy should be initiated with angiotensin converting enzyme (ACE) inhibitors or angiotensin receptor blockers (ARB). If these medications are already present, calcium channel blockers, beta-blockers, or thiazide diuretics may be added.

Subjects whose blood pressure exceeds 140/90 mmHg on 3 consecutive visits and who have undergone dose increases or the addition of antihypertensive medications over each of 3 visits, should be discontinued from study drug and referred back to their primary healthcare provider for more intensive management. Subjects may continue attending study visits off study drug, and if blood pressure control is re-established without requiring excluded medications, subjects may be restarted on study drug.

Subjects whose blood pressure drops below 110/70 mmHg, or who exhibit symptoms associated with low blood pressure during the trial should have their antihypertensive medications reevaluated.

8.8 Treatment of Hypothyroidism

Individuals who experience rapid weight loss sometimes develop signs and/or symptoms of hypothyroidism with or without elevation of TSH. Subjects who develop symptoms of hypothyroidism need not be discontinued from study drug. These subjects should be assessed clinically and with appropriate laboratory testing (TSH, free T3, free T4). Subjects found to be hypothyroid may be considered for thyroid replacement therapy, as appropriate.

9.0 STUDY PROCEDURES

A schedule of study activities by visit is presented in [Appendix 1](#). A detailed list of these activities is provided below.

9.1 Schedule of Visits

9.1.1 Screening Visit (Visit 1, Up to – 4 Weeks)

Activities at the Screening visit are:

- Obtain written parental informed consent and subject assent;
- Obtain written parental informed consent and subject assent for DXA (at selected sites);
- Obtain demographics (including age, gender, race, and ethnicity);
- Obtain medical history (including contraception methods);
- Assess inclusion/exclusion criteria;
- Record concomitant medications;
- Administer PHQ-9 and C-SSRS questionnaires;
- Administer neurocognitive battery (CANTAB) familiarization session;
- Obtain vital signs (blood pressure, heart rate, respiration rate, and temperature);
- Obtain weight and waist circumference measurements;
- Measure height and calculate BMI. If a subject does not meet the BMI criterion for inclusion into the study, no further screening procedures should be undertaken;
- Obtain serum samples for blood chemistry panel, hematology panel, lipid panel, HbA1c, HIV, HCV, HBsAg, TSH;
- Obtain urine sample for routine urinalysis, drug screen, and pregnancy test (female subjects);
- Provide contraception/pregnancy counseling (female subjects); and
- Schedule the Randomization visit within 4 weeks (± 3 days).

9.1.2 Baseline/Randomization (Visit 2, Week 0)

Subjects eligible for treatment will be randomized and have study drug dispensed at visit 2. If a subject is found to be ineligible for participation due to laboratory values, the subject may be notified prior to visit 2. Activities at baseline are:

- Confirm inclusion/exclusion criteria (Section 7.0);
- Administer PHQ-9, C-SSRS, and IWQOL-Kids questionnaires;
- Administer neurocognitive battery (CANTAB);
- Obtain vital signs (blood pressure, heart rate, respiration rate, and temperature);

- Obtain weight and waist circumference measurements;
- Measure height and calculate BMI;
- Record any changes in concomitant medications;
- Record any adverse events reported or observed;
- Perform complete physical examination (include Tanner Staging);
- Perform and evaluate 12-lead ECG;
- Perform urine pregnancy test (female only);
- Perform OGTT for all subjects eligible for participation by results of Visit 1 screening tests (a separate visit may be scheduled for the OGTT) and obtain blood sample for glucose and insulin at 2 hours following oral glucose load;
- Conduct hand and wrist X-ray;
- Conduct DXA measurement (if applicable);
- Contact IWRS to randomize the subject. Dispense study drug and instruct the subject on the proper use of the study drug (Section 8.4.3);
- Provide diet (a 500-calorie/day deficit)/lifestyle modification and contraception/pregnancy counseling (female subjects); and
- Schedule the next study visit in 4 weeks (\pm 7 days).

9.1.3 Treatment Week 4 Through Week 52 (Visits 3 Through 15)

- Obtain weight and waist circumference measurements;
- Administer PHQ-9 and C-SSRS questionnaires;
- Administer neurocognitive battery (CANTAB), Visit 6 only;
- Obtain vital signs;
- Measure height and calculate BMI;
- Record any changes in concomitant medications;
- Record any adverse events reported or observed;
- Perform urine pregnancy test;
- Collect study drug from previous visit, assess treatment compliance, and perform drug accountability; and dispense study medication and instruct the subject in the proper use of the study drug;
- Obtain blood sample for chemistry panel (Visits 3, 4, and 9 only);
- Obtain blood sample for hematology and lipids panel (Visit 9 only);
- Obtain blood sample for HbA1c (Visits 5 and 11 only);
- Provide diet (a 500-calorie/day deficit)/lifestyle modification and

- contraception/pregnancy counseling (female subjects); and
- Schedule the next study visit in 4 weeks (\pm 7 days).

